2.2.2. Secondary Endpoints

The secondary endpoints are:

1. The number and percentage of study participants who after one or two doses of Bris10 M2SR or placebo demonstrate:
 - i. Influenza-specific serum antibody responses measured at specified time points;
 - ii. Influenza-specific mucosal immunoglobulin A (IgA) antibody responses measured at specified time points;
 - iii. Influenza-specific cellular immune responses measured by cytokine enzyme-linked immunospot (ELISPOT) at specified time points.
2. The number and percentage of study participants who after one or two doses of Sing2016 M2SR or placebo demonstrate:
 - i. Influenza-specific serum antibody responses measured at specified time points;
 - ii. Influenza-specific mucosal IgA antibody responses measured at specified time points;
 - iii. Influenza-specific cellular immune responses measured by ELISPOT at specified sampling time points.
3. Vaccine virus shedding evaluated by influenza A-specific qPCR on day 7 post IP administration.

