Each subject will undergo the following testing (also depicted in [Table 3](#)): [Note that a Pre-screen with blood draw to assess the subject's microneutralization (MN) titer to Sing2016 may be conducted under a site-specific ICF in the period spanning 90 calendar days before enrollment in this study.] Subjects who meet eligibility criteria will be enrolled in the proposed Phase 1b study, have a baseline blood draw, be randomized to a dose cohort and administered IP of either active M2SR vaccine or placebo on Days 1 (Visit 01) and 29 (Visit 04). For 7 days following each dose the subjects will record symptoms in a Symptom Memory Aid ([Appendix 5](#)) and after 3 days (Days 4 and 32) will be contacted via a phone call by the site staff representative to report symptoms and AEs. Subjects will attend the investigational site for follow-up on Days 8, 29, 36, 57 and 209 (Visits 03, 04, 06, 07 and 08, respectively) for a limited physical exam, safety evaluation, nasal swabs and blood draws. Day 209 will also be the end of study visit for each subject in the study. Serum samples for analysis of anti-HA antibody titers for the H3N2 antigen in Sing2016 and Bris10 will be collected at baseline and on Days 8, 29, 36, 57 and 209. PBMC samples for analysis of cell-mediated immunity and/or innate transcriptome gene expression will be collected at baseline and on Days 4 (optional), 8, 29, 32 (optional), 36 and 57 from select sites for ~160 subjects. Nasal swabs will be collected on Days 1, 8, 29, 36, 57 and 209 for analysis of IgA-specific anti-HA antibody titers. Nasal swabs will be collected at Days 1, 8, 29, and 36 to evaluate shedding of vaccine virus. A nasal swab collected at Day 1 may be evaluated for presence of respiratory pathogens. Safety clinical laboratory testing will be performed at screening, and on Days 1, 8, 29, and 36. During the treatment period (Day 1 – Day 57), subjects will be asked to notify the site immediately if symptoms of influenza (fever, chills, sore throat, rhinorrhea, cough, muscle/body aches) occur. When increased influenza infections are being reported in the geographic region of the investigational site, subjects will additionally be contacted at Days 15±2, 21±2, 43±2, and 50±2 by phone or messaging. If influenza is suspected the subject will be asked to return to the site for laboratory confirmation of influenza using nasal swabs.

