6. ASSESSMENTS

6.1. Timing of Assessments

An overview of the timing of treatment(s) and assessments is given in the Schedule of Events (Table 3). Details of safety and efficacy assessments are provided in Section 6.2.1 through Section 6.2.3, and Section 6.2.4, respectively.

When visit assessments are planned at the same time point in the study, the order of assessments should be in order of less invasive to more invasive. For example, during the randomization visit, vitals, medical history, pregnancy testing and drug testing should be conducted before blood work and subsequent nasal swab.

Table 3: Schedule of Events

Study Visit Number	V00	V01	V02	V03	V04	V05	V06	V07	V08	Early Term ⁷
Study Day Post-First Dose	Days -30 to -1	Day 1	Day 4 ±1	Day 8 ±1	Day 29 +/- 7	Day 32	Day 36	Day 57	²⁰ Day 209	
Study Day Post-Second Dose					D1	Day 4 ±1	Day 8 -1/+7	Day 29 +/-7	D181 +/-14	
Informed Consent	X									
Inclusion/Exclusion	X	X ²			X ²					
Demography	X									
Physical exam	X ¹									X ⁸
Limited physical exam ¹⁰		X ^{2,4}		X	X ^{2,4}		X	X	X	X ⁹
Medical/medication history	X	X ²			X ²					
Vital signs (height, weight, BP, HR, temp) ¹⁶	X	X ^{2,4}		X	X ^{2,4}		X	X	X	X ⁸
Pregnancy testing (urine)	X	X ³			X ³					
Hematology ⁶	X	X ^{2,5}		X	X		X			X ¹³
Chemistry ⁶	X	X ^{2,5}		X	X		X			X ¹³
Urinalysis (dipstick)	X	X ^{2,5}		X			X			X ¹³
Urine Drug Screen	X									
Serology for HIV, Hep B & C	X									
Symptom Memory Aid ¹¹		X		X	X		X			X
Scripted phone call with site to report symptoms			X			X				
Assessment for influenza ¹⁹		X	X	X	X	X	X	X		
Serum collection (HAI, MN, NAI and ELISA)	X	X ²		X	X ²		X	X	X	X
PBMC collection (CMI) & plasma ¹⁸		X ^{2,15}	X ¹⁷	X ¹⁵	X ^{2,15}	X ¹⁷	X ¹⁵	X		X
Nasal swab for secretory IgA immune response and/or vaccine virus detection	X ¹²	X ^{2,9,12,14}		X ^{9,12}	X ^{2,9,12}		X ^{9,12}	X ¹²	X ¹²	X ^{9,12}
Dose administration		X			X					
Device Weights		X			X					
AEs		X ⁴	X	X	X ^{2,4}	X	X	X		X
Conmeds	X	X ²	X	X	X ²	X	X	X		X
SAEs and medically attended AEs	X	X	X	X	X	X	X	X	X	X

¹Complete Physical is required; neurological, rectal and gynecological exams do not need to be performed unless clinically indicated

²Prior to dosing

³ Pregnancy test by urine dipstick on days 1 and 29 must be negative and reviewed prior to dosing

⁴At 5 (+/- 1) and 30 (+/- 3) min after dosing

⁵ Lab values at Day 1 are considered baseline

⁶Laboratory tests as indicated in Appendix 2.

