6.1.2.6. Day 36 (7 days -1/+7 day after second dose)

- Perform limited physical examination
- Vital signs (blood pressure, heart rate, and temperature)
- Collect blood for serum chemistry and hematology
- Urinalysis (dipstick)
- Symptom Memory Aid reviewed
- Nasal swab into buffer for mucosal IgA and virus shedding
- Collect blood sample for humoral immunogenicity assays (MNT and other serum assays)
- Collect blood sample (PBMC) for cellular immunogenicity assays (ELISpot) – only by select sites
- Collect blood sample (plasma) for cytokine expression – only if PBMC collected by site
- Record concomitant therapy/AEs/SAEs

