8.2.1. Secretory IgA Immune Response and Viral Shedding from Nasal Swab

Summary statistics for secretory IgA immune response (influenza A-specific and total IgA ELISA) at Days 1 (baseline), 29, and 57 post IP administration will be provided.

Summary statistics for viral shedding (influenza A-specific q-PCR) at Screening, Days 1 and 8, will be provided.

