12. CHANGES IN THE CONDUCT OF THE STUDY OR PLANNED ANALYSES

The study was planned to enroll 50 subjects per treatment group. Enrollment was halted at approximately 40 subjects per group due to seasonal flu considerations.

Due to COVID-19 some Day 209 follow-up visits were conducted by telephone.

Secondary and exploratory endpoint data for CMI (ELISPOT) and viral shedding (influenza A-specific q-PCR) data were not available for analysis at database lock.

These and additional exploratory study endpoints may be the subject of future analyses.

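### SAP 8.2.1 plans vaccine-virus shedding for the first dose only, and summarises mucosal IgA without the responder counts that define the protocol's endpoints

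*SAP*

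**What the plan says.** **Shedding, protocol.** Secondary endpoint 3 (Protocol 2.2.2) reads: "Vaccine virus shedding evaluated by influenza A-specific qPCR on day 7 post IP administration". Investigational product is given on Days 1 and 29. Protocol 3.2 states: "Nasal swabs will be collected at Days 1, 8, 29, and 36 to evaluate shedding of vaccine virus". The Day 36 visit list (Protocol 6.1.2.6) includes "Nasal swab into buffer for mucosal IgA and virus shedding". In Table 3, the row "Nasal swab for secretory IgA immune response and/or vaccine virus detection" carries footnote 9 (aliquot for virus detection) at Days 1, 8, 29, 36 and Early Termination. At Screening it carries only footnote 12 (aliquot for IgA).

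**Shedding, SAP.** Section 8.2.1: "Summary statistics for viral shedding (influenza A-specific q-PCR) at Screening, Days 1 and 8, will be provided". Section 12: "Secondary and exploratory endpoint data for CMI (ELISPOT) and viral shedding (influenza A-specific q-PCR) data were not available for analysis at database lock". Section 12 then says that these endpoints may be analysed in future. It gives no time points or method.

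**Mucosal IgA.** Protocol endpoints 1.ii and 2.ii are framed as the number and percentage of participants with a mucosal IgA response after one or two doses. SAP 8.2.1 plans "Summary statistics for secretory IgA immune response (influenza A-specific and total IgA ELISA) at Days 1 (baseline), 29, and 57" after administration. Neither document defines an IgA response.

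**The concern.** Evaluating shedding is a named secondary objective. The protocol supports outpatient conduct with earlier findings that a single 10^8 dose of Bris10 shed no infectious virus. This trial adds a second dose, a vaccine not previously given to humans (Sing2016) and dose levels up to 10^9. Those single-dose data do not cover shedding after dose 2, and the swab that would show it is already scheduled. If the deferred analysis follows 8.2.1 as written, the two-dose trial will report shedding for the first dose only.

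For IgA, the planned tables would describe the distribution of values. A reader could not take from them the quantity that the endpoint names, which is how many participants responded.

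**Working it through.** No sample-size or power figure is involved, so there is no plan figure to reproduce. The check compares lists of days.

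**1. Days that the shedding endpoint requires.** Seven days after dose 1: 1 + 7 = Day 8. Seven days after dose 2: 29 + 7 = Day 36.

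**2. Shedding swabs by source.**

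| Visit | Protocol 3.2 | Table 3 footnotes | Protocol 6.1 visit lists | SAP 8.2.1 shedding |
|---|---|---|---|---|
| Screening | not listed | 12 (IgA) | swab, purpose not stated | yes |
| Day 1 | yes | 9 and 12 | IgA and shedding | yes |
| Day 8 | yes | 9 and 12 | IgA and shedding | yes |
| Day 29 | yes | 9 and 12 | IgA and shedding | no |
| Day 36 | yes | 9 and 12 | IgA and shedding | no |
| Day 57 | not listed | 12 (IgA) | IgA and shedding | no |
| Day 209 | not listed | 12 (IgA) | IgA and shedding | no |

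On-study days in Protocol 3.2 but not in the SAP: {1, 8, 29, 36} minus {1, 8} = {29, 36}. The SAP covers 1 of the 2 day-7 time points. It also lists one visit, Screening, for which Table 3 shows no virus aliquot.

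The table shows a conflict inside the protocol as well. Sections 6.1.2.7 and 6.1.2.8 give the Day 57 and Day 209 swabs a shedding purpose. Section 3.2 and the Table 3 footnotes do not.

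**3. Timing of the Day 36 swab.** The heading of Protocol 6.1.2.6 begins "Day 36 (7 days -1/+7 day after second dose", and Table 3 agrees. That allows 7 - 1 = 6 to 7 + 7 = 14 days after dose 2. Protocol 6.2.1.6 describes the same visit with a window of one day either side, which is 6 to 8 days. Under the wider window, a result labelled Day 36 may come from a swab taken a week later than the endpoint's day 7.

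**4. Culture.** Protocol 6.2.4.1 sends qPCR-positive swabs for quantitative infectious culture. SAP 8.2.1 plans no summary of those results.

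**5. IgA.** Collected on Days 1, 8, 29, 36, 57 and 209; summarised on Days 1, 29 and 57. The summarised days include baseline, after one dose and after two doses, so the gap is in the form of the summary. The at-least-2-fold and at-least-4-fold rates in SAP 8.2 follow a paragraph limited to serum HAI, MN and ELLA. Tables of IgA responders planned: none. SAP 8.2 derives values corrected for total IgA, but 8.2.1 does not say whether its summaries use them.

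**6. Scale, for illustration only.** With 0 positives among n, the two-sided exact 95% upper limit is 1 - 0.025^(1/n).

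- n = 40 (approximate enrolment per group, SAP Section 12): 1 - 0.025^(1/40) = 8.8%.
- n = 50 (planned per group): 1 - 0.025^(1/50) = 7.1%.

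The limit rises as n falls, so dropouts before dose 2 or missed swabs would push it above 8.8%.

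**The case against.** **A reader might infer that two secondary endpoints go unreported, or that dose-2 shedding will never be analysed.** The documents do not support that. Section 8.2.1 plans shedding at Day 8 and IgA after one and two doses. Section 12 discloses that all shedding qPCR data, Day 8 included, were missing at lock and leaves later analysis open. What stands is narrower: the deferral is optional, names no days, and leaves 8.2.1 as the only specification.

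**The SAP matches the protocol's analysis section.** Protocol 8.3.4 asks only for descriptive statistics for mucosal antibody and shedding. That is true, so the IgA mismatch lies partly within the protocol itself. But 8.3.4 does not redefine the endpoints in 2.2.2, and a count with a percentage is itself descriptive.

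**The fold-rise sentence in SAP 8.2 names no assay, so it might be read as covering IgA.** The paragraph that introduces it is confined to the three serum assays, so this reading is strained.

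**A reader might pool four active arms at about 40 each and claim that a bound near 2.3% (0/160) is being lost.** That mixes two vaccines and three Sing2016 dose levels, ignores participants who did not receive dose 2, and says nothing specific to the highest dose. No such bound is planned for Day 8 either. The per-arm figure is the most that can be offered, as an illustration.

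**Nothing in the protocol requires late Day 36 swabs to be excluded.** Correct. Showing them separately is a sensitivity display.

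**Conclusion.** The point holds in this form. SAP 8.2.1 covers endpoint 3 for dose 1 only: one of two post-dose time points, with Days 29 and 36 missing and Screening included without a virus aliquot in Table 3. Section 12 does not repair this. Mucosal IgA is reported, but not as the number and percentage of responders.

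The size is one missing dose-2 shedding result per arm and no IgA responder table. The 8.8% limit assumes zero positives and 40 evaluable swabs in an arm.

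This should be fixed, but it is not critical: the endpoints are secondary and descriptive, no hypothesis is tested, and the primary safety analysis is unaffected. The conclusion rests on reading day 7 after administration as applying to each dose, which the Day 36 swab schedule supports.

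**What to change.** **Shedding.** Amend 8.2.1, or write an addendum governing the deferred analysis, before the data are examined:

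- Report N (%) qPCR-positive, and culture-positive among those, by arm with exact 95% confidence intervals at Day 1 pre-dose, Day 8, Day 29 pre-dose and Day 36.
- Remove Screening.
- Report days since dose 2 for each Day 36 swab, and show swabs taken well after day 7 separately as a sensitivity display, with the cut-off stated in advance.
- Reconcile Protocol 6.1.2.7 and 6.1.2.8 (shedding at Days 57 and 209) with Protocol 3.2 and Table 3, and the Day 36 window in 6.1.2.6 with that in 6.2.1.6.

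**IgA.** Add N (%) of responders by arm at Days 29 and 57, with a stated and justified definition that says whether it uses the value corrected for total IgA. Rises of 2-fold and 4-fold are one option, borrowed from the serum analysis; the documents give no basis for preferring them for IgA. SAP 8.6 allows results by treatment before lock, and the protocol synopsis allows an early review of partial data. If IgA data have already been seen by treatment, label the definition post hoc.

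**Cost.** SAP wording and a few tables. The swabs are already scheduled, and Section 12 indicates that the shedding data had not been available for analysis. The IgA definition needs a short scientific justification.

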8.3. Exploratory

Depending upon the results of primary and secondary analyses, some or all exploratory analyses may not be done.

Cell-mediated immunity (CMI) assessed by frequencies and fold-increases of antigenspecific T-lymphocytes may be summarized. Additional influenza-specific assays may be performed, and results summarized.

Results of exploratory analyses may be reported separately from the CSR.

8.4. Adjustments for Covariates

No adjustments for covariates beyond baseline values are planned.

8.5. Handling of Dropouts or Missing Data

Subjects who are withdrawn from the study will not be replaced.

No missing data will be imputed.

8.6. Interim Analyses and Data Monitoring

There are no planned interim analyses.

Top line results (grouped by treatment) with no subject-level information may be produced prior to data base lock for sponsor review.

8.7. Multiple Comparisons / Multiplicity

There are no formal tests of hypotheses thus no adjustment for multiple tests.

All p-values are descriptive only.

8.8. Examination of Subgroups

There are no planned subgroup analyses.

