10. H3N2 Sing2016 MN titers $\leq 1:20$ (determination within 90 calendar days of study enrollment is acceptable and does not need to be repeated for entry to this study).

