8. STATISTICAL METHODS AND CONSIDERATIONS

8.1. General Considerations

Prior to the analysis of the study data, statistical methods and table shells will be detailed in a Statistical Analysis Plan (SAP) and finalized before database lock.

The final analysis will be done after the last subject has had the day 57 visit and the data base has been locked. The day 209 data will be included as a supplemental analysis.

Statistical analysis will be the responsibility of Northrim Consulting, Inc, using SAS® (SAS Institute Inc., Cary, NC, USA; version 9.4 or higher).

There are primary, secondary and exploratory objectives, endpoints and analyses. Depending upon the result of the primary and secondary analyses, not all exploratory analyses may be done.

Safety and subject disposition analyses will be conducted on the safety analysis set.

Summarization of primary and secondary efficacy endpoints will be done using FAS. These summaries may be repeated using the PP analysis set.

There are no formal tests of hypotheses in this study. Efficacy outcomes are descriptive only.

The data will be summarized in tables listing the number, mean, standard deviation, median, minimum, maximum, standard error (SE) and a 95% CI of subjects for continuous data, or in tables listing count and percentage for categorical data where appropriate. Tables will be presented by IP treatment and overall. Data listing by subject will be provided.

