8.3.4. Additional Analyses

Additional analyses will be descriptive only; p-values are descriptive and not corrected for multiple testing.

Immunogenicity

Serum antibody, mucosal antibody and cellular immune response will be summarized using descriptive statistics by sampling timepoint for all subjects and by baseline values.

Seroconversion rates will be presented by timepoint and by baseline starting values.

Viral shedding will be summarized using descriptive statistics.

Additional (exploratory) endpoints may be analyzed.

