8.2. Secondary

Immunogenicity data sources include influenza-specific serum antibody responses (MN, HAI, ELLA) and mucosal IgA antibody responses as listed below.

External Vendor-supplied data to be integrated into the clinical database.

Vendor Name	Specimen Material Type	ISTESTCD (Test Virus)	ISSCAT (Assay Type)	Comment
Southern Research	SERUM	BRIS	MN	No LLOQ, lowest values reported = 5.
Southern Research	SERUM	SING	MN	No LLOQ, lowest values reported = 5.
Viroclinics	SERUM	BELG	MN	
Viroclinics	SERUM	BRIS	HAI	•

Viroclinics	SERUM	H6N2	ELLA	
Viroclinics	SERUM	KANS	HAI	
Viroclinics	SERUM	KANS	MN	
Viroclinics	SERUM	Hong Kong	НАІ	
Viroclinics	SERUM	Hong Kong	MN	
Viroclinics	SERUM	SING	HAI	
Viroclinics	SERUM	SWTZ	HAI	
Viroclinics	SERUM	SWTZ	MN	
		,	,	
VisMederi	NASAL MUCUS	BRIS	SIgA	LLOQ=3; set to 1.5. At the replicate level.
VisMederi	NASAL MUCUS	SING	SIgA	LLOQ=3; set to 1.5. At the replicate level.
VisMederi	NASAL MUCUS	TOTIGA	SIgA	No LLOQ.
VisMederi	NASAL MUCUS	BRISC= BRIS/TOTIGA	SIgA	BRIS to be corrected for TOTIGA. If TOTIGA <1 then BRISC= missing, otherwise BRISC=BRIS/TOTALIGA.
VisMederi	NASAL MUCUS	SINGC= SING/TOTIGA	SIgA	SING to be corrected for TOTIGA. If TOTIGA <1 then SINGC= missing, otherwise SINGC=SING/TOTIGA

Serum antibody response (influenza-specific HAI, MN, and ELLA results) after one and after both administrations of M2SR vaccine will be summarized by treatment comparisons of GMT, GMFR, seroprotection, and seroconversion (2-fold and 4-fold).

GMTs will be summarized at Days 1, 29, and 57; GMFR will be summarized by Day 29/Day 1, Day 57/Day 1, and Day 57/Day 29. Ln-transformed GMT and the Intransformed GMFR ratios will be analyzed using ANCOVA with baseline (Day 1) values as a covariate. [Note: GMFR Day 57/Day29 is modelled with Day 1 baseline covariate.]

Conversion rates categorized as >=2-fold and >= 4-fold values will be reported for Days 29 and 57. Pairwise comparisons of conversion counts (%) will be done using Fishers Exact Tests.

Seroprotection rates at Days 1, 29 and 57 will be presented for the hemagglutination inhibition (HAI) assay only. Pairwise comparisons of seroprotection counts (%) will be done using Fishers Exact Tests.

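### The SAP omits, without listing it as a change, the protocol's immunogenicity tables by baseline titre and all Day 8, 36 and 209 serology

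*SAP*

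**What the plan says.** **Protocol.** Section 8.3.4 makes two commitments. The general one is "Serum antibody, mucosal antibody and cellular immune response will be summarized using descriptive statistics by sampling timepoint for all subjects and by baseline values". The specific one is "Seroconversion rates will be presented by timepoint and by baseline starting values". Section 3.2 sets the schedule: serum for antibody titres to the H3N2 antigens "in Sing2016 and Bris10 will be collected at baseline and on Days 8, 29, 36, 57 and 209". Section 8.1 says "The day 209 data will be included as a supplemental analysis". Entry is restricted on one baseline titre only, the screening "H3N2 Sing2016 MN titers", which may not exceed 1:20 (4.1). No limit is set for Bris10, the other test strains or any haemagglutination inhibition (HAI) titre.

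**SAP.** Section 8.2 says "GMTs will be summarized at Days 1, 29, and 57" and "Conversion rates categorized as >=2-fold and >= 4-fold values will be reported for Days 29 and 57". Geometric mean fold rise (GMFR) is given for Day 29/Day 1, Day 57/Day 1 and Day 57/Day 29, and HAI seroprotection for Days 1, 29 and 57. Section 8.2.1 limits mucosal IgA to the same three days. No table is split by baseline titre, and 8.8 reads "There are no planned subgroup analyses". Geometric mean titre (GMT) and GMFR are analysed by ANCOVA with the Day 1 value as covariate. Conversion and seroprotection are compared pairwise by Fisher's exact test without adjustment. Section 1.1.2.1 says that randomisation was not stratified on any baseline characteristic. Section 12, which records changes, covers the lower enrolment, telephone visits at Day 209, and the cellular and shedding data that were unavailable at lock. It does not mention serology days or by-baseline tables.

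**The concern.** The trial was set up to find a dose and schedule that makes more vaccinees respond serologically (Protocol 1.1 and 1.4.3), and conversion measures that most directly. Pre-existing immunity matters here by the protocol's own account: section 1.2.3 says it limits the response of most adults to the licensed live vaccine, and section 1.2.4 says M2SR induces responses despite pre-existing antibody, citing animal data. Conversion by baseline titre is where this trial could examine that in people. The sponsor's first-in-human study stratified on baseline HAI (1.4.1). This trial did not, so the tables are the remaining means.

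At stake are three things: whether response varies with starting titre, whether the arms happened to differ in starting titre when conversion is compared, and any six-month antibody result. Because section 12 is silent, a reader of the study report could not tell a deliberate change from an oversight.

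**Working it through.** **Plan's own figure.** There is no power calculation to reproduce. The sample size is empirical: 5 × 50 = 250 planned. At the roughly 40 per group reported in SAP 12, the total is 5 × 40 = 200.

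**Step 1: documents side by side.**

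| Item | Protocol | SAP | Declared in SAP 12? |
|---|---|---|---|
| Conversion by baseline titre | Planned (8.3.4) | None (8.2, 8.8) | No |
| Antibody results by baseline value | Planned (8.3.4) | None; baseline enters only as an ANCOVA covariate | No |
| Serum days | 1, 8, 29, 36, 57, 209 (3.2) | 1, 29, 57 (8.2) | No |
| Day 209 serology | Within the supplemental analysis (8.1) | None | No; only telephone visits are noted |

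The untabulated days are 8, 36 and 209: 3 of 6 serum days, or 3 of 5 after baseline. Days 8 and 36 fall about a week after each dose and show early response. Only Day 209 bears on persistence.

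**Step 2: what unadjusted conversion can hide.** Let q be the share of subjects above a baseline cut-off and g the gap in conversion between the two baseline strata. The documents give neither, so both are assumed. With n = 40 per arm, the 95% range of chance imbalance between two arms is 1.96 × √(2q(1−q)/n):

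- q = 0.5: 1.96 × √(2 × 0.25/40) = 0.219
- q = 0.3 or 0.7: 1.96 × √(2 × 0.21/40) = 0.201

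The shift this causes in the conversion difference is the imbalance times g:

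| Assumed g | Shift in difference |
|---|---|
| 10 points | about ±2 points |
| 30 points | ±6 to 7 points |
| 50 points | ±10 to 11 points |

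The expected imbalance is zero, so this is noise and not bias. It is also part of ordinary sampling error, not an addition to it. At an assumed 50% conversion in both arms, the full 95% range of the difference is 1.96 × √(2 × 0.25/40) = ±21.9 points. With q = 0.5, baseline accounts for a share g² × 0.25/0.25 = g² of that variance: 1%, 9% and 25% for gaps of 10, 30 and 50 points. That is roughly what adjustment could remove.

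**Step 3: what strata can show.** Exact (Clopper-Pearson) 95% intervals at an assumed 50% conversion:

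| n | Interval |
|---|---|
| 40 (whole arm) | 33.8% to 66.2% |
| 20 | 27.2% to 72.8% |
| 10 | 18.7% to 81.3% |

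By-baseline tables are feasible, but as description only.

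**The case against.** The strongest defence has four parts.

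- **Baseline is not ignored.** GMT and GMFR carry the Day 1 titre as a covariate, and entry narrows the Sing2016 microneutralisation range. This stands, but it leaves conversion and seroprotection unadjusted, and the entry limit does not reach the other strains or HAI.
- **Days 29 and 57 answer the objectives.** They give the response after one and two doses. The secondary endpoints leave the time points unspecified, no objective names antibody persistence, and the Day 209 analysis is only supplemental. This limits the importance of the missing days. It does not cover the by-baseline tables, which 8.3.4 promises outright, or the silence in section 12.
- **The analyses are unpowered and descriptive, and small strata give wide intervals.** This is true, and it is a reason to present them descriptively.
- **A model for conversion is not in the protocol.** That is correct: it is an addition. It fits, however, with Protocol 8.3, which foresees baseline variables as covariates, and with SAP 8.4, which permits adjustment for baseline values.

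A reader might infer that conversion rates are confounded by pre-existing immunity. The documents do not support that for the planned comparisons. Arms are randomised, so against any one test strain they share the same expected baseline distribution, whether or not that strain is capped at entry. The argument would have force for conversion compared across test strains, but SAP 8.2 plans treatment comparisons and no cross-strain test.

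A reader might also infer that six-month antibody data are lost. The SAP shows only that no table is planned. Section 12 leaves room for later analyses, though it does not name serology.

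**Conclusion.** The omission is certain from the text: by-baseline immunogenicity and conversion tables, and serology on three of five post-baseline days, are in the protocol, absent from the SAP and undeclared. The consequence is moderate. At about 40 per arm, chance baseline imbalance could move a conversion difference by ±6 to 7 points if strata differ by 30 points, and by ±2 to ±11 points over assumed gaps of 10 to 50. Without the tables, neither that imbalance nor variation by pre-existing titre would be visible in the conversion results.

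These sizes rest on assumed stratum shares of 30% to 70% and assumed gaps, because the documents give no baseline titre distribution. Nothing here affects the primary safety objective. Whether Day 8, 36 and 209 sera were assayed is not stated; the documents show only that collection was scheduled and that some Day 209 visits, being by telephone, could yield no serum.

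**What to change.** 1. **By-baseline tables.** In SAP 8.2, present GMT, GMFR and ≥2-fold and ≥4-fold conversion descriptively by strain-specific Day 1 titre category, with n and exact 95% intervals. Set categories for each strain and assay: a cut at 40, for example, would leave the upper stratum nearly empty for Sing2016 microneutralisation, given entry at no more than 1:20. Reword 8.8 to match.
2. **Adjusted conversion.** Beside each Fisher test, add a comparison adjusted for ln Day 1 titre by logistic regression, with a penalised or exact fit where an arm has few or no converters. Keep it descriptive.
3. **Missing days.** Add descriptive tables for Days 8, 36 and 209 where sera were assayed, with Day 209 limited to on-site visits and its n shown.
4. **Otherwise declare it.** Where any of this is not done, state and justify the omission in section 12.

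**Cost.** Items 1 and 2 use Day 1 titres that the planned fold rises and ANCOVA already need, so they cost programming and extra tables. The price is wide intervals: about 27% to 73% in a stratum of 20 at an assumed 50% conversion. Item 3 is cheap only for sera already assayed. If none were, the 12 serum assay and strain combinations in SAP 8.2 would mean at most 200 × 3 × 12 = 7,200 further results, and declaring the omission may be the reasonable choice.
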